**COMPANY CONFIDENTIAL**

## **11. STUDY PROCEDURES**

### **11.1. Overview**

The Schedule of Activities/Study Flow Chart ([Section 2](#)) summarizes dose administration and the timing and frequency of safety and efficacy procedures and measurements. In the event of abnormal safety findings during the conduct of the study, the attending physician may request additional safety evaluations, either immediately or subsequently at a frequency considered appropriate.

### **11.2. Screening Visit**

Informed consent will be obtained from the subjects before any study related assessments are conducted.

- Inclusion and exclusion criteria
- Demography
- Collection of age
- Significant medical history – the condition, diagnosis, or surgical procedure
- History of medication and other treatments (within 30 days prior to screening)
- Vital signs: resting blood pressure, heart rate, respiratory rate, oral temperature
- Height, weight and BMI assessment
- A serum sample will be collected to test for HIV antibody, hepatitis B surface antigen (HBsAg) and hepatitis C virus antibody (anti-HCV)
- Urine drug screen test
- Urine pregnancy test on females with childbearing potential

Subjects who meet all study entry requirements per the inclusion/exclusion criteria will be scheduled for the dental procedure within 30 days after Screening.

### **11.3. Baseline Visit (Day of Surgery)**

The following will be re-evaluated prior to the surgical procedure, and the evaluations will be recorded in the source documents and the CRF. For data collected on both Screening and Baseline Visits, only the data collected at Baseline will be recorded on the CRF.

- Inclusion and exclusion criteria
- Any changes to medical and surgical history

Test Naproxen Sodium 220 mg Tablet  
Protocol: CCSPAA000457  
Version 1: 11 May 2018  
Version 2: 19 July 2018 - Administrative Change/Non-substantial Amendment 1

- Any changes to prior and concomitant therapies
- Vital signs: resting blood pressure, heart rate, respiratory rate, oral temperature
- Urine drug screen test
- Urine pregnancy test on females with childbearing potential

A negative urine drug screen and urine pregnancy test (for women of childbearing potential) must be obtained on the same day as the surgical procedure.

#### **11.4. Randomization**

After the dental procedure, subjects will be asked to rest quietly at the study center until they experience both post-surgical pain of at least moderate pain on a categorical scale ranging from (0) none to (3) severe and at least a score of 5 on the 11-point (0-10) PI-NRS within 4.5 hours of the last stitch during oral surgery. Subjects who did not meet these criteria will be considered a screen failure.

Randomization numbers will be assigned to subjects in sequential order starting with the lowest available number within the appropriate gender stratum for subjects with moderate baseline pain and starting with the highest available number in the appropriate gender stratum for subjects with severe baseline pain intensity. Randomized subjects will receive their dose of investigational product, which will be considered time 0. The administration of investigational product should occur as described in Section 10.3. Site staff will inspect the subject's oral cavity to ensure that the investigational product was swallowed.

#### **11.5. Post dose Assessments**

Two stopwatches labeled as perceptible and as meaningful will be used to measure "perceptible pain relief" and "meaningful pain relief", respectively. The face of each stopwatch will be covered to prevent the subject from seeing the running clock. Upon dosing, the investigator or the designated site staff will start both stopwatches at the same time. Subjects will only be given the second stopwatch after they stop the first one.

Site personnel will instruct "I would like you to stop the first stopwatch (perceptible) when you first begin to feel any pain relieving effect whatsoever of the drug, that is, when you first feel any pain relief. This does not necessarily mean you feel completely better, although you might, but when you first feel any difference in the pain you have now. As soon as you stop the stopwatch please press your call light to notify the study coordinator. I would like you to stop the second stopwatch (meaningful) when you have meaningful pain relief, that is, when the relief from the starting pain is meaningful to you. As soon as you stop the stopwatch, please press your call light to notify the study coordinator." Upon dosing, the investigator or the designated site staff will start both stopwatches at the same time. Once the stopwatch has been stopped, the investigator or designated study staff will retrieve the stopwatch and record the time in the source documents and CRF. [REDACTED]

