### 10.3. Preparation, Handling and Disposal

Investigational products and placebo will be supplied by the Sponsor in bulk containers in an unblinded manner. In order to maintain the double-blind status of the study, the site must adhere to the following general storage, dispensing, and dosing procedures:

- The site will delegate a qualified third party and back-up staff member(s) who will be responsible for dispensing and administering study medication and who will have no other direct or indirect role in the execution of this study.

Test Naproxen Sodium 220 mg Tablet

Protocol: CCSPAA000457

Version 1: 11 May 2018

Version 2: 19 July 2018 - Administrative Change/Non-substantial Amendment 1

- The Sponsor will provide a randomization schedule directly to the qualified third-party individual. The randomization schedule will be kept in a locked, secured area with access limited to only the assigned third-party individual and un-blinded monitor.
- Covered dosing cups will be used by the assigned third-party dispenser to transport the assigned investigational product from the designated dispensing room to the subject's room.

Investigational product preparation and dispensing will be performed on Day 1, following dental surgery. For subjects who meet the randomization criteria, an independent third-party dispenser will administer one of the following study treatments with up to 180 ml of water at ambient temperature to blindfolded subjects:

- a single 440-mg dose of naproxen sodium as two Test NPX 220 mg tablets
- a single 440-mg dose of naproxen sodium as two commercial [REDACTED] 220 mg tablets
- a single 440-mg dose of naproxen sodium as two commercial [REDACTED] 220 mg capsules, or
- a single dose of two placebo tablets

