Baseline pain assessments and drug administration will be completed in the subject's room. The third-party dispenser will prepare study medication for each subject in a designated dispensing room. Study medication will be dispensed at the time that the subject's pain level is determined to be eligible by verbal assessment, just prior to the completion of the baseline categorical pain severity scale and the baseline 11-point [0-10] pain intensity numerical rating scale [PI-NRS]. The study coordinator will communicate the subject's pain severity and gender to the dispenser. The dispenser will assign the next available randomization number from the appropriate stratum. The dispenser will dispense the appropriate study treatment from the appropriate bulk supply containers into an individual dosing cup. The double-blind label with the same randomization number will be affixed to the dosing cup and the tear-off portion of the label will be attached to the patient's source documents. The third-party dispenser will complete the study drug dispensing record. The study drug dispensing record will remain in a secure and locked area, with access limited to the unblinded third-party dispenser, back-up staff member, and un-blinded monitor. A second individual, with no other study involvement, will witness the preparation and dispensing process. No other study personnel will be present in the designated dispensing room at the time of study drug dispensing. The dispenser will ensure the dosing cup containing the randomized study treatment is covered prior to exiting the dispensing room.

The third-party dispenser will inform the blinded study coordinator once the study drug is dispensed and is ready to be administered to the subject. Following completion of the baseline categorical pain severity scale and baseline pain intensity numerical rating scale, the study coordinator will blindfold the subject and then exit the subject's room to inform the dispenser that the pain assessments are completed and confirm that the pain severity has not changed from the verbal assessment used to determine the appropriate randomization, and

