**COMPANY CONFIDENTIAL**

Test Naproxen Sodium 220 mg Tablet

Protocol: CCSPAA000457

Version 1: 11 May 2018

Version 2: 19 July 2018 - Administrative Change/Non-substantial Amendment 1

that the pain intensity numerical rating scale score qualifies the subject for randomization. If the baseline categorical pain severity has changed, new study drug from the corresponding pain stratum will be prepared and the randomization number and study medication corresponding to the original pain stratum will not be reused. The dispenser will deliver the study drug from the designated dispensing room to the subject's room in a covered dosing cup to ensure no other individual will be able to see the study drug in the bottle. No other study personnel, other than the third-party witness, will be present in the subject's room at the time of dosing.

After entering the blindfolded subject's room and while the subject is sitting up, the dispenser will hand the dosing cup containing the study treatment to the blindfolded subject and instruct the subject to empty the contents of the dosing cup directly into their mouth and then swallow the study medication immediately with up to 180 ml of water at ambient temperature. The dispenser will inspect the subject's oral cavity to ensure that the study treatment was swallowed. The time at which the subject swallows the study medication will be recorded as Time 0. Study drug will be administered to the subject within 5 minutes of the completion of the baseline pain assessments.

If a subject vomits after dosing, the subject will not be re-dosed but will remain in the study.

At the end of the study, the Sponsor will provide instructions as to disposition of any unused investigational product. If the Sponsor authorizes destruction at the study site, the investigator must ensure that the materials are destroyed in compliance with applicable environmental regulations, institutional policy, and any special instructions provided by the Sponsor. Destruction must be adequately documented.

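### Do Protocol sections 10.3 and 11.5 contradict each other on who starts the stopwatches that time the primary endpoint?

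*Protocol*

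**What the plan says.** Protocol section 11.5 assigns the task: "Upon dosing, the investigator or the designated site staff will start both stopwatches at the same time". The instruction appears twice in that section. Once a watch has been stopped, the investigator or designated study staff retrieve it and record the time.

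Protocol section 10.3 describes the dosing itself and does not mention stopwatches:

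- **Dispenser.** "The site will delegate a qualified third party and back-up staff member(s) who will be responsible for dispensing and administering study medication", a person "who will have no other direct or indirect role in the execution of this study".
- **Witness.** "A second individual, with no other study involvement, will witness the preparation and dispensing process".
- **Coordinator.** Once the baseline pain scales are complete, "the study coordinator will blindfold the subject and then exit" the room.
- **Who is present.** "No other study personnel, other than the third-party witness, will be present in the" room when the dose is taken.
- **After the swallow.** "The dispenser will inspect the subject's oral cavity to ensure that the study treatment was swallowed".
- **Origin of the time scale.** "The time at which the subject swallows the study medication will be recorded as Time 0".

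Protocol section 11.4 refers to section 10.3 for administration and gives the mouth inspection to site staff.

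Protocol section 14.6.1 and SAP section 5.3.1 take TCPR from the first stopwatch, in minutes. Subjects without relief, or who take rescue or discontinue before relief, are censored at 12 hours. Protocol section 14.7.2 and SAP section 5.3.2 look for the earliest separation from placebo in one-minute steps, working back from 45 minutes.

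**The concern.** Taken word for word, the two sections seem to leave nobody to start the watches. The blinded coordinator has left. The dispenser is barred from any role beyond dispensing and administering, and the witness from any other involvement. The investigator is not among those allowed in the room. One way out is for blinded staff to start the watches after they come back in. The watch zero would then be later than the swallow, and every recorded time to relief would be too short by that gap.

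In most trials a few seconds would not matter. Here the primary endpoint is the watch reading itself, the planning median for the test tablet is only 17 minutes (Protocol section 14.1), and the secondary result is a single minute found in one-minute steps. No visible text adjusts the reading back to Time 0. An unclear clock start could therefore affect the onset figures that are the point of the study. A lag that differed by arm could also bias the comparisons.

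**Working it through.** **1. Can the passages be read together?**

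| Question | Section 10.3 | Sections 11.4 and 11.5 |
|---|---|---|
| Is the dispenser site staff? | Delegated by the site | 11.4 gives site staff the mouth check that 10.3 gives the dispenser |
| Who can observe the swallow? | Only the dispenser and witness are with the subject | 11.4 also sets time 0 at dosing and refers to 10.3 |
| Who starts the watches? | Not addressed | Investigator or designated site staff, at dosing |
| Who retrieves and reads them? | Not addressed | Investigator or designated study staff, once stopped |

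The protocol's own usage counts the dispenser among site staff. The swallow time must be recorded as Time 0, and only the dispenser and witness are there to see it. Noting that moment is therefore already part of giving the dose, and pressing start at the same moment is a natural extension of it. The role descriptions are also not exhaustive: the witness is introduced for preparation and dispensing, yet is later placed in the room for dosing. On this reading section 11.5 is met, nobody else enters the room, and the lag is zero.

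**2. What if there were a lag?**

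Let *d* be a lag common to all arms, in minutes. A recorded event time becomes *t* − *d*, and censored subjects stay at 12 × 60 = 720 minutes.

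- Two events: (*t*₁ − *d*) − (*t*₂ − *d*) = *t*₁ − *t*₂, so their order is unchanged.
- An event and a censored subject: *t* − *d* < *t* ≤ 720, so the event still comes first.
- Two censored subjects: still tied at 720.

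The Wilcoxon statistic depends on the data only through this ordering, so it does not move.

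A simulation agrees. It used 200 data sets of 150 test and 50 placebo subjects, with exponential times at the planning medians of 17 and 120 minutes. It assumed that 20% of test and 50% of placebo subjects never confirmed relief. At lags of 5 seconds and 1 minute, the largest change in the Wilcoxon Z was 0. The test-arm median fell by exactly the lag (0.083 and 1.0 minute).

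**3. What would move?**

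Only absolute times move. The documents give no lag, so the range below is an assumption. Formula: lag ÷ 17.

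| Assumed lag | Share of the 17-minute median |
|---|---|
| 0 | 0% |
| 5 s (5/60 = 0.083 min) | 0.083/17 = 0.5% |
| 30 s (0.5 min) | 0.5/17 = 2.9% |
| 1 min | 1/17 = 5.9% |

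Subjects counted as relieved by recorded minute *m* are those truly relieved by minute *m* + *d*. The earliest-separation minute therefore shifts earlier by about *d*, at most about one step in this range. Under a common lag the difference between the planning medians is unchanged: (120 − *d*) − (17 − *d*) = 103 minutes.

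**The case for a change.** The strongest case for acting is that starting the clock for the primary endpoint is not plainly dispensing or administering, so the zero-lag reading strains the clause that gives the dispenser no other role, direct or indirect. A cautious site could decide that only blinded staff may touch the watches and start them on re-entry. The remedy would be one sentence. Sensitivity analysis 1 in SAP section 5.3.1 adds a further argument. It censors at the time of rescue, and if that time runs from dosing while relief runs from the watch, the two scales could have slightly different origins, so the invariance shown for the primary analysis does not strictly carry over.

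Some of this stands. The text does not say outright who presses start, and a clarifying sentence would do no harm. The rest does not amount to a flaw. Section 10.3 gives the task to nobody, so section 11.5 is not contradicted, only left to be applied. The sentence proposed would write down the reading the protocol already supports. The visible text does not state the origin of the rescue time, so the sensitivity-analysis point is a possibility and not an error. Nothing visible suggests a lag that differs by arm, or a broken blind. There is also redacted text next to the stopwatch instructions in section 11.5 and around both definitions of TCPR, so the absence of a visible rule is weak evidence that none exists.

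Correcting each reading by the clock time of the watch start minus Time 0 is not clearly a gain either. The documents state neither the precision of Time 0 nor any clock synchronisation. If Time 0 were recorded only to the minute, which is an assumption, the correction could add more error than a lag of 5 to 30 seconds.

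**Conclusion.** The concern does not call for a change. The protocol leaves an operational detail implicit, and sections 10.3, 11.4 and 11.5 are consistent if the dispenser, as delegated site staff, starts both watches at the swallow and the investigator or designated study staff retrieve and read them. The lag is then zero.

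If a site did otherwise, a lag common to all arms would leave the primary Wilcoxon tests exactly as they are. The reported median onset and the earliest-separation minute would each be early by the lag: 0.5% to 5.9% of the 17-minute planning median, and at most about one one-minute step, over an assumed range of 5 seconds to 1 minute. This rests on the lag being the same in every arm, which nothing visible contradicts, and on censoring at 12 hours as both documents define it. Following the plan as written still supports sound conclusions about the test tablet against placebo and the two commercial products.

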**COMPANY CONFIDENTIAL**

([APPENDIX 1](#))

Subjects who use rescue therapy will continue in the study ([APPENDIX 2](#)).

### **11.6. Follow-Up Phone call**

Subjects will be interviewed by telephone to follow up on appropriate postsurgical medical care and changes in their health, including any emergent or existing AEs. The interview will occur between Day 6 – 10. At least three attempts should be made to contact the subject by phone. If the subject cannot be contacted by phone by Day 10, then a certified letter should be mailed to the subject. Every effort will be made by the investigator or designated study staff to adhere to the schedule. Additional postsurgical medicines (e.g., antibiotics or analgesic prescriptions) or therapies (e.g., ice packs) that are taken after the 12-hour [REDACTED] will be recorded on the subject's source documents, but not in the CRF; however concomitant medications and other treatments taken for or associated with an AE will be recorded on the CRF and the source documents. Emergent or existing AEs will be recorded in both the source documents and CRF.

## 12. ASSESSMENTS

### 12.1. Efficacy Assessments

[REDACTED]. Evaluations will include the following parameters:

- Pain intensity
  - Four-point categorical scale collected at baseline: (0) no pain; (1) mild pain; (2) moderate pain; (3) severe pain
  - 0-10 PI-NRS collected at baseline [REDACTED]
- [REDACTED]
- Time to perceptible pain relief – recorded using stopwatch perceptible
- Time to confirmed perceptible pain relief is defined as the time to perceptible pain relief, provided that the subject subsequently stopped the second stopwatch indicating meaningful pain relief.
- [REDACTED]
- [REDACTED]
- [REDACTED]

### 12.2. Safety Assessments

Safety will be monitored via AE reporting. If an AE is reported, the subject will be asked to elaborate on the nature of the event. The investigator or designated study staff will evaluate and record according to the AE Reporting section of the protocol.

Normal consequences of dental surgery (e.g., pain, swelling, bruising) are not considered AEs unless the investigator believes the condition worsened or was aggravated following study drug therapy.

### **12.2.1. Physical Examination**

Height and weight measurements will be collected at screening and BMI will be calculated.

### **12.2.2. Vital Signs**

Vital signs will be collected at screening and baseline. All vital signs (blood pressure, pulse, respiratory rate, and oral body temperature) will be collected after at least 5 minutes of rest in a supine or semi-reclining position in a quiet setting without distractions (e.g., television, cell phones). Systolic and diastolic blood pressure and pulse rate measurements will be assessed with a completely automated device, consisting of an inflatable cuff and an oscillatory detection system. All values will be registered on an automated recorder so that measurements are observer independent. Manual techniques will be used only if an automated device has malfunctioned. Respiratory rate will be measured over at least 30 seconds. Oral body temperature will be measured using a Sponsor-approved standard method. Abnormal vital signs collected at screening and baseline will be assessed by the medically qualified investigator to confirm that the subject is medically suitable for study participation.

### **12.2.3. Clinical Laboratory Tests**

Females of childbearing potential will have a urine pregnancy at screening visit and at baseline. Serology will be performed at screening and will include HIV antibody, hepatitis B surface antigen (HBsAg) and hepatitis C virus antibody (anti-HCV). A urine drug screen will also be performed at screening and baseline. The minimum requirements for urine drug testing include cocaine, tetrahydrocannabinol, opioids (e.g., buprenorphine, oxycodone, methadone, and morphine), benzodiazepines, and amphetamines.

## **13. ADVERSE EVENTS**

Timely, accurate, and complete reporting of safety information from clinical studies are crucial for the protection of subjects, Investigators, and the Sponsor, and are mandated by regulatory agencies worldwide. All observed or volunteered AEs regardless of suspected causal relationship to the Investigational Product(IP) will be reported as described in the following sections. For all AEs, the Investigator or medically qualified individual (MD/DO/DMD/DDS) must pursue and obtain adequate information to make the appropriate assessments.

### **13.1. Definitions**

#### **13.1.1. Definition of Adverse Event**

An AE is any untoward medical occurrence that occurs in a subject after they have signed an informed consent for a study. The event does not need to have a suspected causal relationship with the IP. Therefore, an AE can be any unfavorable and unintended sign, symptom, disease or injury temporally associated with the subject's participation in the study. Examples of AEs include, but are not limited to:

- Abnormal test findings,
- Clinically important signs and symptoms,
- Changes in physical examination findings,
- Hypersensitivity, and
- Progression/worsening of underlying disease.

Additionally, they may include the signs or symptoms resulting from:

- Overdose,
- Withdrawal,
- Abuse,
- Drug misuse,
- Drug interactions,
- Medication errors,
- Product dependency,
- Exposure *in utero*, and
- Study related procedure

